2.3.8 Pharmacokinetic Assessments

Entinostat

Blood samples for determination of entinostat levels will be collected pre-dose and 2 to 4 hours post-dose on Cycle 1 Day 1; anytime post-dose on Cycle 1 Day 8, Cycle 2 Day 1, and Cycle 4 Day 1; and pre-dose on Cycle 2 Day 8. These samples will be collected in both the Phase 1b and Phase 2 portions of the study. On each sample collection day, the time and date of entinostat administration, the start and stop time of avelumab administration, and the time and date of PK sample collection should be recorded in the eCRF.

Avelumab

Blood samples for determination of avelumab levels and avelumab antidrug antibodies (ADAs) will be collected pre-dose and immediately prior to the end of infusion (PK only) on Day 1 of Cycles 1 through 6, then Day 1 of Cycles 8, 10, 12, 16, 20, 28, 32, 36, and 48, at EOT, and at the 30-day Follow-up. Samples must be drawn within 2 hours prior to the start of avelumab infusion, but before any drug (i.e., entinostat) is given. These samples will be collected in both the Phase 1b and Phase 2 portions of the study. Samples should be taken from the arm contralateral to the infusion arm. On each sample collection day, the time and date of entinostat administration, the start and stop time of avelumab administration, and the time and date of sample collection should be recorded in the eCRF.

2.3.9 Safety Assessments

The following assessments will be performed to evaluate the safety profile of entinostat and avelumab. The assessments will be performed during Screening, on Day 1 of each cycle, at the EOT visit (7 days post-last dose) and at the Safety Follow-up visits, as described in the Schedule of Study Assessments (Protocol Table 1-1).

- Vital signs: temperature, pulse rate, and blood pressure (systolic and diastolic)
- Body height (at screening only) and weight
- 12-lead Safety ECGs are recorded at the Screening Visit, and as clinically indicated throughout the study as outlined in the Schedule of Study Assessments
- AE and SAE recording
- Hematology: white blood cell (WBC) count with differential, red blood cell (RBC) count, platelet count, hemoglobin (HGB) and hematocrit (HCT), coagulation studies, including prothrombin time or international normalized ratio (PT/INR) and activated partial thromboplastin time (aPTT; at Screening only)
- Chemistry: alanine transaminase (ALT), aspartate transaminase (AST), alkaline phosphatase (ALP), albumin, total bilirubin, blood

urea nitrogen (BUN), calcium, creatinine, electrolytes (sodium, potassium, magnesium [Mg at Screening only; thereafter as clinically indicated], chloride, bicarbonate), glucose, lactate dehydrogenase (LDH), phosphorus, total protein, thyroid stimulating hormone (TSH), adrenocorticotropic hormone (ACTH; Screening only) and thyroxine (T4)

2.3.10 Other Assessments

Other assessments include patient demographics, epithelial ovarian cancer history, prior systemic anti-cancer therapy, prior surgery related to ovarian cancer, prior radiation therapy, medical history, physical examinations, entinostat administration and accountability, avelumab administration and accountability, concomitant medications and procedures, protocol deviations, post-treatment anti-cancer therapy, ECOG performance status score, and clinical disease assessment, collected per Schedule of Study Assessments (Protocol Table 1-1).

3 STATISTICAL METHODS

3.1 General Methods

3.1.1 Computing Environment

The statistical analyses performed for this study will be presented by study phase. For the Dose Determination phase, tabulations will be provided by dose cohort and overall. For the expansion phase, tabulations will be provided by treatment arm. Some analyses may be performed based on both phases combined.

All statistical analyses will be performed using SAS® Version 9.4 or higher for Windows. Programming specifications will be prepared, which describe the datasets and variables created for this study. The datasets will be prepared using the most recent version of CDISC's Study Data Tabulation Model (SDTM) and Analysis Dataset Model (ADaM).

3.1.2 Reporting of Numerical Values

Descriptive statistics (n, mean, standard deviation, median, minimum, and maximum) will be calculated for continuous variables. Frequencies and percentages will be presented for categorical and ordinal variables. Percentages will be based on the number of patients with non-missing assessments. If there are missing values, the number missing will be presented, but without a percentage.

Means and medians will be reported to one decimal place more than the data reported in the clinical data management system. Standard deviations will be reported to two decimal places more than the data reported. Minimum and maximum will be reported to the same to the same number of decimal places displayed in the clinical data management system.

3.1.3 Baseline Value and Change from Baseline

Baseline will be defined as the most recent, non-missing value obtained immediately prior to the first dose of any study drug (entinostat or avelumab). Change from baseline will be calculated by subtracting the baseline value from the on-study assessment for each patient (i.e., post-dose – baseline).

3.1.4 Handling of Missing/Incomplete Values

Unless otherwise specified, missing data will not be imputed. For AE start dates, the first algorithm described below will be used to determine treatment emergence. For incomplete dates of diagnosis, the second algorithm described below will be used to determine the incomplete date if the day and/or month is missing.

Algorithm for Imputation of Incomplete/Missing Adverse Event Start Dates

Case 1:

if year portion of AE start date = missing then missing AE start date = dose date;

Case 2:

if year portion of AE start date = year portion of dose date
then do;

if month portion of AE start date = missing

then missing AE start date = dose date;

else if month portion of AE start date = month portion of dose date

then missing AE start date = dose date;

else if month portion of AE start date \neq month portion of dose date

then missing AE start date = mdy(AE start month, 1, AE start year);

end;

Case 3:

If year portion of AE start date $>$ year portion of dose date, then AE is treatment-emergent.

Algorithm for Imputation of Incomplete/Missing Date of Diagnosis

If the date of diagnosis is missing the day and/or month, the following algorithm will be used.

Case 1:

For cases where day and month are unknown or missing, the day and month will be set to June 30 with the known year, provided that the resulting date is before treatment start date. Otherwise, one day prior to treatment start date (treatment start date – 1) will be used.

Case 2:

For cases where only the day is unknown or missing, the day will be set to 15 with the non-missing month and year, provided the resulting date is before the treatment start date. Otherwise, one day prior to the treatment start date (treatment start date – 1) will be used.

3.2 Analysis Sets

3.2.1 Full Analysis Set

The Full Analysis Set (FAS) will serve as the primary population for the analysis of PFS and other efficacy-related endpoints in the Phase 2 portion of the study. The FAS will include all patients who are randomized in Phase 2 by following intent-to-treat principle. Patients will be grouped according to the treatment group to which they were randomized (entinostat + avelumab or avelumab only). Patients in this set will be analyzed according to the treatment they were randomized to receive, regardless of any errors in dosing.

3.2.2 Per-Protocol Analysis Set

The Per-Protocol Analysis Set is a subset of the FAS. The Per-Protocol Analysis Set consists of all patients who do not violate the terms of the protocol in a way that would majorly impact the study outcome. All decisions to exclude patients for the Per-Protocol Analysis Set will be made prior to the unblinding of the treatment arms for the final analysis.

3.2.3 Safety Analysis Set

Without otherwise specified, the Safety Analysis Set will be used for the analysis of safety data in both the Phase 1b and Phase 2 portions of the study. The Safety Analysis Set will include all patients who received at least one dose of either study drug, entinostat, or avelumab. Patients will be included in the treatment group corresponding to the study drug they actually received. For most patients this will be the treatment group to which they were randomized. Patients who took incorrect study drug for the entire treatment period will be included in the treatment group corresponding to the study drug they actually received. At least one laboratory or vital sign measurement obtained, subsequent to at least one dose of study treatment, is required for inclusion in the analysis of a safety specific parameter. To assess change from baseline, a baseline measurement is also required.

3.2.4 Pharmacokinetic Analysis Set

Patients will be evaluable for the primary PK analysis if they receive the reference agent administered with and without the other agent. Additionally, patients must have sufficient plasma concentration-time data from each treatment period in order to provide for meaningful assessment of the PK parameters (e.g., AUC and C_{max}). The PK Analysis Set will include all patients who have evaluable plasma concentration-time data for each treatment period, and for whom one or more of the designated PK parameters can be determined.

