1 INTRODUCTION

Clinical Trial SNDX-275-0603 is a Phase 1b/2 evaluating the combination of entinostat with avelumab in patients with advanced epithelial ovarian cancer. The study consists of 2 phases: an open-label Safety Lead-in (Phase 1b) and an Expansion Phase (Phase 2). The Expansion Phase evaluates the efficacy and safety of entinostat with avelumab, when administered at the recommended Phase 2 dose (RP2D), versus avelumab plus placebo in patients with epithelial ovarian cancer in a randomized, double-blind, placebo-controlled setting. Up to 138 patients are anticipated if the study completes all phases of evaluation (up to 18 patients for Phase 1b; up to 120 patients for Phase 2). In Phase 2, patients are randomized in a 2:1 ratio to receive either avelumab plus entinostat or avelumab plus placebo, respectively. The randomization for the Phase 2 portion is to be stratified by the presence of bulky disease (defined as presence of a tumor ≥ 50 mm) versus not, and by a history of progression while on primary platinum treatment, or within 1 month from completion of primary platinum-containing regimen, versus not.

This SAP contains a detailed description of the data presentations and statistical analyses that will be included in the clinical study report for Protocol SNDX-275-0603. The statistical methods and analyses described here are based on those presented in the study protocol.

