2.1.2 Secondary Objectives

Efficacy: To evaluate the efficacy of entinostat in combination with avelumab in patients advanced epithelial ovarian cancer, as determined by:

- PFS based on immune response RECIST (irRECIST)
- Overall response rate (ORR) (i.e., complete response [CR] or partial response [PR]) based on RECIST 1.1 and irRECIST
- Clinical benefit rate (CBR) (i.e., CR, PR, or stable disease [SD] for at least 24 weeks) based on RECIST 1.1 and irRECIST
- Overall survival (OS)

In patients with best overall confirmed response of CR or PR:

- Duration of response (DOR)
- Time to response (TTR)

Pharmacokinetics: To assess the effect of entinostat on the pharmacokinetics (PK) of avelumab

Safety: To evaluate safety and tolerability of entinostat in combination with avelumab, as measured by adverse events (AEs) and clinical laboratory parameters

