2.2.2 Secondary Endpoints (analyzed for the same populations as the primary endpoint)

- PFS by irRECIST
- ORR (CR or PR) by RECIST 1.1 and irRECIST
- CBR (CR, PR, or SD for at least 24 weeks) by RECIST 1.1 and irRECIST
- OS
- DOR and TTR (in patients who experience best overall response of CR or PR)
- The effect of entinostat on the PK of avelumab

Safety:

- Determination of DLTs, MTD, and RP2D
- Incidence of treatment-emergent adverse events (TEAEs), serious adverse events (SAEs), AEs resulting in the permanent discontinuation of study drug, and deaths occurring within 30 days of the last dose of study drug
- Changes from baseline in laboratory, vital signs, Eastern Cooperative Oncology Group (ECOG), physical examination, and electrocardiogram (ECG) values

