2.3.4 Study Drug Treatment

A treatment cycle is defined as 2 weeks (14 days) in length. The dose of avelumab will be 10 mg/kg, administered intravenously (IV) over 1 hour every 2 weeks (Day 1 of each cycle), for all patients. Entinostat (during the Phase 1b Safety Lead-in) and entinostat/placebo (during Phase 2, Expansion Phase) will be administered orally (PO) on Days 1 and 8 of each 14-day cycle. The Safety Lead-in will begin with a starting dose (Dose Level 1) of entinostat 5 mg PO weekly. If Dose Level 1 exceeds the MTD

(i.e., if at least 2 patients experience a DLT), accrual to this dose cohort will be terminated and entinostat 3 mg PO weekly (Dose Level -1) will be investigated. If Dose Level -1 exceeds the MTD, then entinostat 2 mg PO weekly (Dose Level -2) will be investigated. Dosing is planned to be continuous unless interrupted for management of an AE. Each dose level will be reviewed by the Sponsor Study Physician(s) in consultation with the Investigators after the majority of the safety assessments for each level are completed. The entinostat dose determined appropriate for combination with avelumab will then be taken forward into the Phase 2 Expansion Phase of the study as the RP2D. Up to 120 patients with advanced epithelial ovarian cancer will be randomized to receive avelumab with entinostat or placebo in a 2:1 allocation in the Phase 2 Expansion Phase.

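### The PK Analysis Set (SAP Section 3.2.4) uses crossover conditions in a parallel-arm trial: with avelumab as reference agent, 0 of up to 138 patients meet them by design

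*SAP*

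**What the plan says.** Section 3.2.4 of the SAP has three sentences. The first sets who counts for the primary PK analysis: "Patients will be evaluable for the primary PK analysis if they receive the reference agent administered with and without the other agent". The second adds that there must be enough concentration data from each treatment period to assess the PK parameters. The third defines the set itself: "The PK Analysis Set will include all patients who have evaluable plasma concentration-time data for each treatment period", provided at least one designated PK parameter can be determined. The reference agent is not named.

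The PK objective in Section 2.1.2 is "To assess the effect of entinostat on the pharmacokinetics (PK) of avelumab", and Section 2.2.2 lists the matching secondary endpoint.

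On design, Section 1 says: "In Phase 2, patients are randomized in a 2:1 ratio to receive either avelumab plus entinostat or avelumab plus placebo, respectively". Section 2.3.4 gives avelumab on Day 1 of each cycle to all patients. Of entinostat or placebo it says that it "will be administered orally (PO) on Days 1 and 8 of each 14-day cycle", and it adds: "Dosing is planned to be continuous unless interrupted for management of an AE".

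**The concern.** Receiving an agent both with and without a second agent, with data from each period, is a within-patient requirement. It belongs to a crossover or sequential interaction study. Here the contrast that bears on the PK objective is between patients: avelumab with entinostat in one arm, avelumab with placebo in the other.

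The avelumab summaries in Tables 14.2.1.2 and 14.2.2.2 carry the PK-set tag in Section 6.1, and Section 3.3.2 plans mean concentration plots by treatment. If the set follows the first sentence, these outputs lose every correctly dosed placebo patient, who are the only randomized source of avelumab data without entinostat. What remains is a group selected after randomization, namely patients whose entinostat was interrupted or stopped while avelumab went on. Such a set could not show entinostat's effect on avelumab PK.

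**Working it through.** **Inputs (planned maximum numbers)**
- Section 1: up to 18 patients in Phase 1b, up to 120 in Phase 2, up to 138 in all; Phase 2 allocation 2:1.
- Section 2.3.1: 80 on entinostat and 40 on placebo in Phase 2; 6 to 12 more patients may be accrued; Phase 1b will include between 6 and 18.
- Section 2.3.4: the dosing days given above. No run-in, crossover or single-agent period is described.
- Sections 2.1.2 and 2.2.2: the question is entinostat's effect on avelumab, so avelumab is taken as the reference agent (an inference).

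**The plan's own figures**
- 18 + 120 = 138.
- 120 × 2/3 = 80 and 120 × 1/3 = 40. Both agree with the SAP.

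**Planned exposure to avelumab**

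| Group | Planned n | With entinostat | Without entinostat | Both, by design |
|---|---|---|---|---|
| Phase 1b | 18 | 18 | 0 | 0 |
| Phase 2, entinostat | 80 | 80 | 0 | 0 |
| Phase 2, placebo | 40 | 0 | 40 | 0 |
| Total | 138 | 98 | 40 | 0 |

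Every avelumab infusion in a combination patient is scheduled on a day when entinostat is also due, because Day 1 of each cycle is common to both drugs. Correctly dosed placebo patients never receive entinostat.

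**Other sizes**
- With 6 or 12 extra patients the total is 138 + 6 = 144 or 138 + 12 = 150; the last column stays 0.
- With 6 patients in Phase 1b the total is 6 + 120 = 126; the last column stays 0.

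**Who could qualify in practice.** Only a patient whose entinostat was interrupted or stopped while avelumab continued. The SAP gives no expected number.

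**The other reading.** If the third sentence stands alone and each patient has a single treatment period, up to 138 patients could enter the set, including up to 40 on placebo. The placebo column of the avelumab tables is therefore 0 on one reading and up to 40 on the other.

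**The case against.** The strongest reply is that only the third sentence defines the set. It does not repeat the with-and-without condition, and in it the word evaluable describes data, not patients. Section 3.2.3 speaks of a single treatment period ("Patients who took incorrect study drug for the entire treatment period"), so one period per patient is a possible reading, and on it both arms enter. This has some force: it shows that the literal outcome is not the only one. It does not rescue the text. Asking for data in each treatment period implies more than one, and the first sentence's rule for the primary PK analysis still cannot be met as the trial is designed.

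No analysis elsewhere in the SAP is called the primary PK analysis, so the first sentence may be leftover wording. That is plausible, and is a reason to remove it.

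The reference agent is inferred. If it were entinostat, Day 8 doses fall on days without an avelumab infusion, and on a same-day test up to 98 patients would meet the first sentence. But no avelumab-free period is planned, that reading does not serve the stated objective, and correctly dosed placebo patients would still be excluded.

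Section 3.11 leaves details to a separate analysis plan, which is not at hand. That plan may use another set, but the SAP does not say so. Its own tables carry the PK tag.

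**Conclusion.** The concern holds. Section 3.2.4 is wrong as written for this design. With avelumab as the reference agent, 0 of up to 138 patients satisfy the first sentence by design; 98 receive avelumab only with entinostat and 40 only without.

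The count rests on three assumptions: avelumab is the reference agent, patients are dosed as scheduled, and the planned maximum numbers apply. The extra accrual and the smaller Phase 1b do not change the zero. The effect on the tables depends on which sentence is taken to govern, and the SAP does not settle that.

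The damage is confined to a secondary PK objective and its outputs. The primary PFS analysis and the safety analysis are unaffected. The section should be corrected, so that the PK population is not left to be chosen outside the written plan.

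**What to change.** In Section 3.2.4, delete the with-and-without condition and the each-treatment-period conditions. Possible replacement text:

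> The PK Analysis Set is defined separately for entinostat and avelumab. For each analyte it includes all patients who received at least one dose of that analyte and have at least one evaluable concentration of it after the first dose; later pre-dose troughs count. Patients are grouped by treatment received. Summaries of a PK parameter include only those patients in the set for whom that parameter can be determined.

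The new text should also say what makes a concentration evaluable, and in particular whether a value below the quantifiable limit counts, since Section 3.3.2 treats some of these as zero and others as missing. Section 3.11 should state that the separate PK plan uses this set.

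Under this definition up to 138 patients could enter the avelumab set, and the Phase 2 comparison could draw on up to 80 with entinostat and 40 with placebo.

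Two extras are separable from the error. The Section 2.2.2 heading ties all secondary endpoints, PK included, to the populations of the primary endpoint; that could be limited to the efficacy endpoints. The separate plan could also give a between-arm geometric mean ratio for avelumab trough and end-of-infusion concentrations.

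The cost is SAP wording and one cross-reference. No new data, visits or samples are needed.

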3.3 Analysis Variables

3.3.1 Efficacy Variables

Efficacy variables include:

- PFS as determined by RECIST 1.1 and irRECIST
- ORR (CR or PR) by RECIST 1.1 and irRECIST
- CBR (CR, PR, or SD for at least 24 weeks) by RECIST 1.1 and irRECIST
- OS
- DOR and TTR (in patients who achieve a best overall response of CR or PR)

3.3.2 Pharmacokinetic Variables

The following PK parameters for the plasma concentrations of entinostat or avelumab will be calculated via non-compartmental methods and summarized, where applicable, using the WinNonlin™ software package (WinNonlin™ Phoenix, Version 6.3, Pharsight Corporation, Mountain View, CA).

Pharmacokinetic variables include:

- C_{max} , maximum plasma concentration
- T_{max} , time at which maximum plasma concentration was observed
- AUC_{0-t} , area under the plasma concentration-time curve from time zero to the last measurable concentration
- AUC_{0-inf} , area under the plasma concentration-time curve from time zero extrapolated to infinity
- $t_{1/2}$, elimination half-life
- λ_z , terminal elimination rate constant

All measurable plasma concentrations will be used for the analysis. For concentration values reported as no Results/not Reportable (NR), values will be treated as missing. Values below the quantifiable limit (BQL) that occur prior to the first measurable concentration will be treated as zero. All other BQL values will be treated as missing.

The mean plasma concentration over time by treatment and the individual subject plasma concentration versus time data will be plotted. Nominal times will be used for plotting the mean plasma concentrations over time by treatment. Actual sampling times will be used for the individual figures and for the non-compartmental analysis.

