3.11 Pharmacokinetic Analysis

A population PK analysis will be used to describe the PK of entinostat. The effects of patient factors (e.g., demographics, clinical chemistries, and disease) on entinostat PK will be evaluated. In addition, the relationship between entinostat exposure parameters and indicators of safety will be assessed. Descriptive statistics will be used to summarize the PK of avelumab and anti-avelumab antibodies at each cycle and time point.

Specific details for these analyses as well as analyses of trough avelumab levels and anti-avelumab antibodies will be provided in a separate analysis plan.

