6.1 List of Tables

Table Number	Title
Table 14.1.1	Analysis Populations
Table 14.1.2A	Study Disposition – Phase 1b
Table 14.1.2B	Study Disposition – Phase 2 (FAS)
Table 14.1.3A	Demographics and Baseline Characteristics – Phase 1b
Table 14.1.3B	Demographics and Baseline Characteristics – Phase 2 (FAS)
Table 14.1.4	Ovarian Cancer Disease History – Phase 2 (FAS)
Table 14.1.5	Prior Adjuvant/Neoadjuvant Therapy – Phase 2 (FAS)
Table 14.1.6	Prior Chemotherapy – Phase 2 (FAS)
Table 14.1.7	Prior Radiation Therapy – Phase 2 (FAS)
Table 14.1.8	Concomitant Medications – Phase 2 (FAS)
Table 14.2.1.1	Summary Statistics for Entinostat Plasma Concentrations (PK)
Table 14.2.1.2	Summary Statistics for Avelumab Plasma Concentrations (PK)
Table 14.2.2.1	Summary Statistics for Pharmacokinetic Parameters of Entinostat (PK)

Table 14.2.2.2	Summary Statistics for Pharmacokinetic Parameters of Avelumab (PK)
Table 14.3.1.1	Entinostat Dosing – Phase 2 (FAS)
Table 14.3.1.2	Avelumab Dosing – Phase 2 (FAS)
Table 14.3.2.1	Entinostat Dosage Modifications – Phase 2 (FAS)
Table 14.3.2.2	Avelumab Dosage Modifications – Phase 2 (FAS)
Table 14.3.3A	Progression Free Survival (RECIST 1.1) – Phase 2 (FAS)
Table 14.3.3B	Progression Free Survival (RECIST 1.1) – Phase 2 (PP)
Table 14.3.3C	Progression Free Survival (irRECIST) – Phase 2 (FAS)
Table 14.3.3D	Progression Free Survival (irRECIST) – Phase 2 (PP)
Table 14.3.3E	Progression Free Survival (RECIST 1.1) – Sensitivity Analysis 1: Forward-Dating PFS Assessment Time – Phase 2 (FAS)
Table 14.3.3F	Progression Free Survival (RECIST 1.1) – Sensitivity Analysis 2: Subsequent Anti-Cancer Therapy as PFS event – Phase 2 (FAS)
Table 14.3.3G	Progression Free Survival (RECIST 1.1) – Sensitivity Analysis 3: Censoring for Subsequent Anti-Cancer Therapy – Phase 2 (FAS)
Table 14.3.4	PFS Multivariate Cox Proportional Hazards Model – Phase 2 (FAS)

Table 14.3.5A	PFS by presence of bulky disease (defined as presence of a tumor ≥ 50 mm) (yes vs. no) – Phase 2 (FAS)
Table 14.3.5B	PFS by platinum based therapy (resistant, refractory and sensitive) -Phase 2 (FAS)
Table 14.3.5C	PFS by history of progression while on primary platinum treatment or within 1 month from completion of primary platinum-containing regimen versus not -Phase 2 (FAS)
Table 14.3.5D	PFS by number of prior platinum based therapies (< 2, ≥ 2) – Phase 2 (FAS)
Table 14.3.5F	PFS by disease stage at initial diagnosis (stage II, stage III/locally advanced, stage IV) - Phase 2 (FAS)

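### Section 3.3.2 promises six non-compartmental PK parameters for both drugs, but the Section 2.3.8 sampling cannot support most of them and Section 3.11 plans different methods

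*SAP*

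**What the plan says.** **Parameters.** SAP Section 3.3.2: "The following PK parameters for the plasma concentrations of entinostat or avelumab will be calculated via non-compartmental methods"; the sentence goes on to limit their summary to where it applies. Six parameters follow: Cmax, Tmax, AUC0-t, AUC0-inf, t1/2 and λz. The section does not say which parameter applies to which drug. Actual times are to be used for the non-compartmental work. For the mean profiles, "Nominal times will be used for plotting the mean plasma concentrations over time by treatment".

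**Outputs.** Section 6.1 lists Tables 14.2.2.1 (entinostat parameters) and 14.2.2.2 (avelumab parameters). Section 6.3 lists PK-parameter listings for both drugs, numbered 16.2.2.3 and 16.2.2.4.

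**Entinostat sampling, Section 2.3.8.** "Blood samples for determination of entinostat levels will be collected pre-dose and 2 to 4 hours post-dose on Cycle 1 Day 1"; then "anytime post-dose on Cycle 1 Day 8, Cycle 2 Day 1, and Cycle 4 Day 1; and pre-dose on Cycle 2 Day 8". The same scheme applies in both phases, and no intensively sampled subset is described. Under Section 2.3.4, entinostat or placebo "will be administered orally (PO) on Days 1 and 8 of each 14-day cycle".

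**Avelumab sampling, Section 2.3.8.** Pre-dose and end-of-infusion samples on Day 1 of Cycles 1 to 6, then of Cycles 8, 10, 12, 16, 20, 28, 32, 36 and 48, with further samples at EOT and at the 30-day follow-up. Avelumab is a 1-hour infusion every 2 weeks.

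**Methods, Section 3.11.** "A population PK analysis will be used to describe the PK of entinostat". Avelumab is to be summarised descriptively by cycle and time point, with details in a separate plan. Section 3.11 does not mention non-compartmental analysis.

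**PK Analysis Set, Section 3.2.4.** Patients must have received the reference agent both with and without the other agent, and must have enough data in each treatment period for parameters such as AUC and Cmax.

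**The concern.** Non-compartmental estimates need a sampled profile: several points around the peak for Cmax and Tmax, coverage of the interval for AUC, and at least three points on the declining limb for a λz whose fit can be judged. The scheme in Section 2.3.8 looks designed for a population model, not for this.

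If Section 3.3.2 were programmed as written, a sampling time could be tabulated as Tmax, an arbitrary post-dose entinostat concentration as Cmax, and a small part of the exposure as AUC0-t. The effect of entinostat on avelumab PK is a secondary objective and endpoint, so its designated parameters should be ones that the samples can yield. The SAP also describes two different PK analyses, in Sections 3.3.2 and 3.11, without saying which governs.

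**Working it through.** The SAP gives no PK sample size or target precision, so there is no figure to reproduce. The check counts samples per dosing interval and then sizes the consequences.

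**1. Entinostat, 168-hour interval.** Each sample is assigned to the dose that it follows.

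| Dose | Post-dose samples in the interval | Count |
|---|---|---|
| C1D1 | 2–4 h | 1 |
| C1D8 | one, untimed | 1 |
| C2D1 | one untimed, plus C2D8 pre-dose (about 168 h) | 2 |
| C2D8 | none | 0 |
| C4D1 | one, untimed | 1 |

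The C1D8 sample is drawn after the second dose, so it does not extend the first-dose profile. Consequences:

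- Where there is one post-dose sample, Cmax is its value and Tmax is its time.
- After dose 1, AUC0-t covers 2/168 = 1.2% to 4/168 = 2.4% of the interval.
- Share of AUC0-inf accrued by time t, assuming immediate absorption and mono-exponential decline with half-life h: 1 − exp(−ln2·t/h). For h = 12 hours this is 10.9% at 2 h and 20.6% at 4 h. For h = 100 hours it is 1.4% and 2.7%. The SAP gives no half-life; this range is an assumption.
- No interval has three points. In the C2D1 interval a line through two points leaves 2 − 2 = 0 residual degrees of freedom, and the untimed sample may precede the peak. λz, t1/2 and AUC0-inf cannot be credibly estimated.

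**2. Avelumab, 14-day interval.**

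- Cycles 1–5: end of infusion plus the next pre-dose sample = 2.
- Cycle 6 and each later sampled cycle: end of infusion only = 1, because the next cycle is not sampled. If that dose is the last, the EOT sample makes 2.

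The end-of-infusion sample is the expected peak of a 1-hour infusion, so Cmax is usable. Tmax is then the infusion time. A two-point λz again has 0 residual degrees of freedom, and t1/2 and AUC0-inf inherit that.

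**3. Avelumab AUC from two points.** Assume mono-exponential decline over T = 336 − 1 = 335 h, with k = ln2/(24·h) for half-life h in days.

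- True area: C0(1 − e^(−kT))/k.
- Linear trapezoid: C0·T(1 + e^(−kT))/2.
- Ratio, linear to true: kT(1 + e^(−kT)) / [2(1 − e^(−kT))].

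| Assumed half-life (days) | 3 | 4 | 6 | 10 | 14 |
|---|---|---|---|---|---|
| Linear/true | 1.746 | 1.446 | 1.208 | 1.077 | 1.039 |

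Example at 3 days: kT = 0.6931 × 335/72 = 3.225 and e^(−kT) = 0.0398, so the ratio is 3.225 × 1.0398/(2 × 0.9602) = 1.746.

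- Log trapezoid: (C1 − C2)·T/ln(C1/C2) = C0(1 − e^(−kT))·T/(kT), which equals the true area. The bias is 0%.

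Section 3.3.2 names the software but not the rule, so the bias runs from 0% to about 75% over these assumptions.

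**4. After the last avelumab dose.** Section 2.3 puts EOT within 7 days of the last dose and the first follow-up 30 ± 7 days after EOT, so about 23 to 44 days after the last dose. If that dose fell in a sampled cycle, a patient can have three points: end of infusion, EOT and follow-up.

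**5. Nominal-time plots.** A sample allowed at any time after the dose has no nominal time, so three of the five entinostat sampling days cannot be placed on the mean profile as specified.

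**6. PK Analysis Set.** Both agents start on Cycle 1 Day 1, and the comparison with placebo is between parallel arms. By design no patient has a period with the reference agent alone and another with the combination, so Section 3.2.4 does not fit this trial.

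**The case against.** Several points on the other side have force.

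- **The commitment is qualified.** Section 3.3.2 limits the summaries to where they apply, Section 3.2.4 demands sufficient data, and Section 3.11 defers details to a separate plan. Blank cells are therefore likelier than false values. This stands in part. But none of these provisions says which parameters fall away, and none withdraws the tables or listings.
- **A reader might infer that the avelumab terminal parameters can be derived in no patient.** The documents do not support that: the EOT and 30-day samples can give some patients three points. Those points come after the last dose, usually with drug carried over from earlier doses, and only in patients whose last dose fell in a sampled cycle. They do not support routine parameter tables by arm.
- **A reader might take the 75% as a property of the plan.** It is not. It needs a linear rule and a 3-day half-life, neither of which the SAP states. What stands is that the rule is unspecified. Under a linear rule the bias varies with half-life, so it would not cancel between arms if entinostat altered clearance.
- **A reader might extend the Cmax criticism to avelumab.** It applies only to entinostat.
- **A reader might infer damage to the exposure–safety analysis.** Section 3.11 places that analysis directly after the population PK model, so model-based exposure is the natural reading. The avelumab summary there is by time point, not by AUC.

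**Conclusion.** The point holds, within limits. On the sample counts alone, with no outside assumption, all six non-compartmental parameters for entinostat are either not estimable or artefacts of the sampling time. For avelumab, Cmax is sound, Tmax carries no information, λz, t1/2 and AUC0-inf have no assessable fit within a dosing interval, and interval AUC depends on an unstated rule. Section 3.3.2 and the planned outputs conflict with Section 3.11, and only 3.11 suits the samples.

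The half-lives, immediate absorption and mono-exponential decline are assumptions used only to size the error; the counts do not rest on them.

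It would go too far to conclude that the PK tables must be wholly empty or wrong, or that the efficacy conclusions are touched. The avelumab table would be partly valid, and no hypothesis test or efficacy endpoint uses these parameters. The effect is confined to secondary, descriptive PK reporting. The correction should be made, but it is not critical to the trial.

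**What to change.** Align Section 3.3.2 with Section 3.11:

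- **Entinostat:** delete all six non-compartmental parameters. Report the observed 2–4 h C1D1 and pre-dose C2D8 concentrations, and take exposure measures from the population model.
- **Avelumab:** report end-of-infusion and trough concentrations by arm and cycle. Delete routine non-compartmental Tmax, AUC0-inf, λz and t1/2. At most, allow an exploratory half-life after the last dose in patients with three points, labelled as such. If an interval AUC is kept for Cycles 1–5, name the trapezoidal rule and state that it rests on two points.
- **Plots:** show the untimed entinostat samples against actual time after dose and leave them out of nominal-time means.
- **Outputs:** revise Tables 14.2.2.1 and 14.2.2.2 and both PK-parameter listings. Identify the listings by title, because Section 6.3 uses the numbers 16.2.2.3 and 16.2.2.4 twice.
- **Section 3.2.4:** redefine the PK Analysis Set for a parallel-arm comparison with sparse sampling, dropping the requirement for each patient to have the reference agent with and without the other agent.

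The cost is SAP wording in two sections, two table shells and two listing shells. No new samples or data fields are needed, since Section 2.3.8 already has dosing and sampling times recorded in the eCRF.
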